6.0 Data Management Plan

6.1 Data Analysis

Analysis of the data in this study will follow the approach described in Wellek, S., and M. Blettner (2012). The following steps are required:

1. Baseline analysis to check the assumption of negligible carryover effects. This test has to be performed like an ordinary unpaired t-test

- .2. Test for differences between treatment effects. Formally, this test is carried out according to the same scheme as the pre-test. The crucial difference is that the customary formula for the unpaired t-test are now applied to the within-subject differences
- 3. Significance decisions: The significance of the difference between two treatments (tDCS and sham) is determined as well as the significance of carryover effects (step 1).

These steps are described in more detail below.

Baseline Analysis

For descriptive purposes, summary statistics of the demographic and outcome variables will be calculated. To ensure pre-stimulation (i.e., baseline) equivalence between participants assigned to the two treatment orders (i.e., sham-active vs. active-sham), the outcome measures obtained during the first baseline period (first baseline assessment session) between these groups will be compared using independent *t*-test comparisons. The primary dependent variable will be the BRIEF; fixed factors will be the treatment order (active-sham versus sham-active), and treatment condition (active and sham condition) and the secondary dependent variable will be the PDDBI. We note that, as described previously, the BRIEF will be used to assess executive functioning and the PDDBI is used to differentiate ASD from other conditions as well as to assesses the effectiveness of treatments in terms of Response to Interventions (RTI). The goal of this baseline assessment is to establish the equivalence of the two groups prior to intervention on the basis of the two outcome assessments.

In addition to summary statistics for the baseline assessments, nonlinear EEG features will be computed before testing for all subjects. Machine learning classifiers will be used to demonstrate that the two groups are equivalent and cannot be distinguished based on nonlinear EEG analysis (see [name] et al., 2018).

Hypothesis Testing

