As described briefly above, an unpaired t-test is applied to the within-subject differences for the outcomes of interest. We note that two summary outcome scores can be used (BRIEF and PDDBI), as well as for subscores. Because the subscores and the total scores are not independent, a Bonferroni correction is likely too strict and not warranted. Total scores and subcategory scores on each assessment will be tested for significant changes over time. The dependent or outcomes to be measured for within-subject differences within each group assignment (or treatment order: active-sham versus sham-active), treatment condition (active versus sham), and time (baseline and 4-week follow-up) will be the dependent variables. Independent variables will be group assignment, treatment condition, and time. The differences over time in either active or sham condition will be carried out using independent measures ANOVA. For all analyses, *P* values less than 0.05 will be considered statistically significant. Analyses were completed using standard R software.

EEG as a Biomarker for Treatment Outcome

The signal or time series from each sensor will be decomposed into multiple frequency bands using a wavelet transform (Walker, 2008). We note that the Haar wavelet transform yields a multiscale decomposition that is mathematically equivalent to the coarse-graining procedure first introduced by (Costa, Goldberger, & Peng, 2005) for multiscale entropy analysis of biological signals. The use of wavelets for multiscale signal decomposition and relationship of scale to traditional EEG frequency bands is discussed in ([name] et al., 2018). Using the wavelet transform, each sensor signal will be decomposed into power-of-two frequency bands that are approximately equal to the commonly used definitions of delta, theta, alpha, beta, gamma, and gamma+ bands used for EEG analysis. The specific software used for the wavelet transform is publicly available, along with instructions and python code, at: https://pywavelets.readthedocs.io.

Several nonlinear values will be computed on multiple scales for every sensor, including sample entropy, Lyapunov exponents, detrended fluctuation analysis (DFA), and correlation dimension (CD). These will be computed on multiple scales using publicly available software "Nonlinear measures for dynamical systems" or nolds, version 0.3.2, which can be downloaded from (https://pypi.python.org/pypi/nolds).

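### The added ANOVA of change over time is specified as independent-measures with no child term, although condition and time both vary within the same child

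*Combined protocol and SAP*

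**What the plan says.** The design is a two-period crossover (section 1.3, Experimental Design; section 1.6 A): each child receives both active and sham stimulation. The parent completes the BRIEF and the PDDBI five times, at weeks 4, 8, 12, 16 and 20 (Table 2).

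Section 6.1 specifies two kinds of outcome analysis.

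- **The treatment comparison.** In step 2, "the customary formula for the unpaired t-test are now applied to the within-subject differences". In step 3, "The significance of the difference between two treatments (tDCS and sham) is determined as well as the significance of carryover effects".
- **Change over time.** Under Hypothesis Testing, "Total scores and subcategory scores on each assessment will be tested for significant changes over time", and "The differences over time in either active or sham condition will be carried out using independent measures ANOVA". The factors are given as follows: "Independent variables will be group assignment, treatment condition, and time". For all analyses, P "values less than 0.05 will be considered statistically significant".

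No child effect, repeated-measures ANOVA or mixed model appears anywhere in section 6.1. The sentence before the factor list opens by referring to within-subject differences but ends by saying that "treatment condition (active versus sham), and time (baseline and 4-week follow-up) will be the dependent variables". Condition and time are therefore named as both dependent and independent variables.

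**The concern.** An independent-measures ANOVA assumes that the rows are independent. Here a child supplies up to four rows (two conditions, two times), and these rows are correlated. Without a child term, stable differences between children stay in the residual. Tests of within-child effects (time, condition, and their interaction) are then judged against too large an error. The between-child factor (order) is judged against too small a one, because four correlated rows count as four independent children.

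At stake are the standard errors, P values and significance statements that this ANOVA produces for BRIEF and PDDBI totals and subscores. The plan does not label the ANOVA as supportive, and it applies the 0.05 threshold to all analyses.

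**Working it through.** **Inputs from the documents.** Section 1.3 recruits 24 children and expects 4 dropouts; section 4.3 requires 20 to complete. The arithmetic agrees: 20 / (1 − 4/24) = 24. The plan gives no power, effect size or SD to reproduce (section 1.5: pilot).

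**Assumptions.** 10 + 10 completers, two-sided 5%, and within-child correlation ρ = 0.3, 0.5, 0.7 or 0.8 (the documents give none). Compound symmetry unless stated, score variance 1, and no period or carryover effect.

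**Reading 1: raw scores, follow-up at weeks 8 and 16.** The order × condition × time model has 80 rows, 8 cells and 72 residual df, and its residual variance estimates 1.

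- *Condition-by-time* (active change minus sham change). True variance is 4(1 − ρ)/20; the ANOVA uses 4/20. Its SE is too large by 1/√(1 − ρ): 1.20, 1.41, 1.83, 2.24. The same factor applies to the time main effect.
- *Order.* The mean of a child's four scores has variance (1 + 3ρ)/4; the ANOVA uses 1/4. Its SE is too small by √(1 + 3ρ): 1.38, 1.58, 1.76, 1.84. The approximate false-positive rate is 2[1 − Φ(1.96/√(1 + 3ρ))] = 15.5, 21.5, 26.6, 28.8%.

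Simulation agrees. For the power row, the true effect is set so that the unpaired t-test on within-child differences (18 df) has 80%.

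| ρ | 0.3 | 0.5 | 0.7 | 0.8 |
|---|---|---|---|---|
| Type I error, time (nominal 5%) | 2.0% | 0.8% | 0.1% | 0.02% |
| Power, condition-by-time (t-test 80%) | 72% | 56% | 29% | 11% |
| Order falsely significant (nominal 5%) | 15% | 21% | 26% | 29% |

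With AR(1) correlation per 4 weeks instead, the order error is 17, 24 and 27% at ρ = 0.5, 0.7 and 0.8.

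**Reading 2: change scores, two rows per child, condition as a factor.** The result depends on which weeks count as follow-up.

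- *Weeks 8/16.* The changes are Y8 − Y4 and Y16 − Y12. Under compound symmetry their covariance is ρ − ρ − ρ + ρ = 0, so type I error is nominal (simulated 5.0%; AR(1) 5.9–6.2%).
- *Weeks 12/20.* The changes are Y12 − Y4 and Y20 − Y12, so week 12 enters both. The covariance is ρ − 1 − ρ + ρ = −(1 − ρ) and each variance is 2(1 − ρ), giving a correlation of −0.5. The true variance of a child's difference is 6(1 − ρ); the ANOVA assumes 4(1 − ρ). The SE ratio is √(4/6) = 0.82 and type I error is about 2[1 − Φ(1.96 × 0.82)] ≈ 11% (simulated 10.6–11.2%; AR(1) 7.1–9.3%).

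**Reading 3: one change score per child within one condition, compared between orders.** Type I error is 4.8–5.2%. This is valid, but it tests order, not the change over time that the sentence names.

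**Which weeks?** Section 1.6 B uses outcomes at the end of each phase, which Table 2 places at weeks 8 and 16. The step list in section 1.3 puts an assessment after each 4-week washout, which is weeks 12 and 20. The EEG paragraph also schedules a recording four weeks after treatment, though that concerns EEG only. Section 6.1 does not choose.

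**Comparator.** The unpaired t-test on within-child differences holds 4.7–5.3% in every setting simulated for ρ = 0.5, 0.7 and 0.8 (both correlation structures, both sets of weeks). Its active-minus-sham estimate is identical to the ANOVA's in the balanced case.

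**The case against.** The strongest reply is that the decision on tDCS versus sham does not rest on this ANOVA. Steps 2 and 3 of section 6.1 assign it to the unpaired t-test on within-subject differences, which removes the child effect. That stands. A reader might infer that the main comparison is invalid; the documents do not support this.

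Second, the text refers to within-subject differences, so raw scores are not certainly what is meant. That also stands in part. But a baseline/follow-up time factor is redundant once change is the outcome, and with condition as a factor there are still two rows per child. Raw scores are the likelier reading, not an established one. The near-nominal result for change scores also depends on the weeks, which are not named.

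Third, a reader might infer that the ANOVA mostly misses real change. At correlations of 0.3 and 0.5 it keeps 72% and 56% power against 80%, so this holds only at higher correlations. For time and condition effects on raw scores at weeks 8/16 the error is conservative and does not manufacture efficacy.

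Fourth, a reader might infer that the inflated order test would corrupt the judgement on carryover. Section 6.1 gives that judgement to a separate unpaired t-test, and nowhere is the ANOVA's order term used for it.

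Pilot status and the absence of a power claim lower the stakes. They do not make the stated error term correct.

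**Conclusion.** The concern holds for the added ANOVA only. As written, it names no child term for data in which condition and time repeat within child. On the raw-score reading its tests of time and condition-by-time are too conservative and its test of order is too liberal, by the amounts tabulated. On the change-score reading it is about right at weeks 8/16 and rejects too often at weeks 12/20.

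The sizes rest on 20 completers split equally, the stated correlation structures, and correlations that are assumptions because the documents give none. The direction on the raw-score reading at weeks 8/16 holds for any positive correlation under compound symmetry. The treatment t-test is sound in this respect and the point estimate is unchanged. This should be fixed, because a stated analysis is wrong on its likelier reading and the repair is small.

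**What to change.** 1. Delete the independent-measures ANOVA sentence. Alternatively, replace it with a paired test within each condition, or with a repeated-measures or mixed model that has a random child effect and fixed effects for sequence, period and treatment (plus time if raw scores are used).
2. State that the unpaired t-test on within-subject differences is the decisive tDCS-versus-sham test.
3. State which weeks the 4-week follow-up refers to, because the ANOVA's error depends on it, and correct the sentence that lists condition and time as dependent variables.

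The cost is SAP wording and a few lines of R. No new data or visits are needed.

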1.6 Study Variables

Expiration Date:

Protocol Title: A Pilot Study of Transcranial Direct Current Stimulation in Children with ASD

A. Independent Variables, Interventions, or Predictor Variables

Subjects will continue to receive their ABA therapy provided by their regular therapist as standard of care. Subjects will be randomized to begin with either sham or tDCS treatment and then cross over to the other treatment arm. Each subject with receive tDCS or sham however the order will be different in the two groups. The active tDCS and sham are procedurally identical.

B. Dependent Variables or Outcome Measures:

AIM 1: The following data will be used as outcome measures at the end of each phase of the study.

Primary The use of rating scales, completed by parents and teachers, measuring overt behavior is an often used and well-established method for assessing various domains of social, emotional, and behavioral functioning and treatment outcomes. As we are targeting the prefrontal areas, the primary outcome measure will be the **Behavior Rating Inventory of Executive Function (BRIEF)**, a test that has normative data for children aged 2 to 90 years. It has parent versions containing 63 (preschool age) 86 (school age) items, taking approximately 10 to 15 minutes to complete. Each item score is converted within each scale for computation of T scores. The BRIEF contains eight subdomains of executive function: 1) Inhibit, 2) Shift, and 3) Emotional Control subdomains together result in an additional composite Behavioral Regulation Index (BRI). The subdomains 4) Initiate, 5) Working Memory, 6) Plan/Organize, 7) Organization of Materials, and 8) Monitor provide a composite Metacognition Index. The BRI and MI are also combined to obtain an overall Global Executive Composite (GEC).

Secondary

Our secondary outcome measure will be the **Pervasive Developmental Disorder Behavior Inventory (PDDBI)** and the Discrete Trial Training (DTT) data from the participant's ABA programs.

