Nonlinear values derived from Recurrence Quantitative Analysis (RQA) will be computed. RQA is an empirical approach to analyzing time series data that is in principle capable of characterizing all the essential dynamics of a complex system. It has been found to be useful for analyzing "real-world, noisy, high dimensional data" (Webber & Zbilut, 2005). Software for computing recurrence plot statistics is publicly available python package pyRQA 0.1.0 (Marwan, 2012). At least seven of the most commonly used recurrence plot values (RR, DET, LAM, L_max, L_entr, L_mean, and TT) will be computed and used in this study. These values have proven to be potential biomarkers for autism ([name] et al., 2018) and absence epilepsy ([name] et al., 2017) in our previous studies.

EEG analysis will first determine significant group differences between actual and sham tDCS for each of the nonlinear signal features computed. We hypothesize that significant changes will be observed in the nonlinear signal features. A Bonferroni correction will be required for the set of nonlinear measures. In addition to feature comparisons, regression models will be computed using the nonlinear EEG features as input variables and the change in assessment scores as output. Linear regression and machine learning regression models will be used.

Taken together, these analyses will provide the information necessary to determine if tDCS significantly improves the efficacy of behavioral therapy for improving cognitive function in children with ASD. In addition, the usefulness of EEG as a tool for measuring the changes in brain function due to tDCS augmented behavioral therapy will be determined.

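### The EEG regression has no stated guard against overfitting in at most 20 to 24 children, its output can confuse tDCS response with ABA gain, and the baseline classifiers cannot show equivalence

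*Combined protocol and SAP*

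**What the plan says.** Section 1.6 (Aim 2) takes EEG from 19 electrode positions in 30-second segments and refers to a cited 2018 study for the feature values and bands. Section 6.1 (EEG as a Biomarker for Treatment Outcome) splits each signal by wavelets into bands approximating six named ones. It then states that "Several nonlinear values will be computed on multiple scales for every sensor", naming four measures, and adds "At least seven of the most commonly used recurrence plot values", naming seven.

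Two analyses follow:
- Active and sham are compared "for each of the nonlinear signal features computed", and "A Bonferroni correction will be required for the set of nonlinear measures".
- In addition, "regression models will be computed using the nonlinear EEG features as input variables and the change in assessment scores as output". The method is given as "Linear regression and machine learning regression models will be used".

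Section 4.3 gives 24 children enrolled and 20 to complete. Section 4.7 C lets a child who does not tolerate the EEG stay in the study without it. Sections 1.1 B (Aim 2) and 1.2 ask whether pre-treatment EEG predicts response to tDCS, or whether EEG is associated with improvement. Sections 1.5 and 1.6 say the EEG biomarker data should help justify an adequately powered trial.

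On possible outputs, section 1.6 says "The BRIEF contains eight subdomains of executive function", plus two indices and a composite, and lists ten PDDBI domains. Section 6.1 (Hypothesis Testing) says "Total scores and subcategory scores on each assessment will be tested for significant changes over time".

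Section 6.1 (Baseline Analysis) also plans machine learning classifiers on baseline EEG to establish that the two treatment orders are equivalent.

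**The concern.** There are three linked weaknesses.

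1. **Overfitting.** There are far more candidate features than children, and the available text gives no rule that separates a real relation from a fitted one. A good in-sample fit is then expected from noise alone.
2. **The output.** All children continue ABA throughout and are expected to gain from it. If the output is change in the active period, or change pooled over both periods, a feature that predicts who gains from ABA will look like a predictor of response to tDCS. The crossover gives each child a sham control, but the plan does not say that the regression uses it.
3. **The baseline classifiers.** Failure to classify is treated as evidence of equivalence.

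At stake is whether an uninformative or purely prognostic EEG feature is carried into the next trial as a tDCS biomarker.

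**Working it through.** **Sample size.** The plan's figure reproduces: 4 blocks x 6 = 24, and 20 completers + 4 dropouts = 24. No feature count, effect size or power is stated for the EEG regression.

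**Feature count.** Inputs: 19 sensors (section 1.6); six named bands, four measures and seven recurrence values (section 6.1).

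| Reading | Formula | Features |
|---|---|---|
| Two scales only, recurrence values once | 19 x 2 x 4 + 7 | 159 |
| Six bands, recurrence values once | 19 x 6 x 4 + 7 | 463 |
| Six bands, recurrence values per sensor | 19 x 6 x 4 + 19 x 7 | 589 |
| All 11 measures per sensor and band | 19 x 6 x 11 | 1,254 |

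At n = 24, 463 features are 463/24 = 19.3 per child. At n = 20, even 159 are 159/20 = 8.0 per child.

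**All features in one linear model, pure noise.** With an intercept, the centred data have rank at most n - 1, which is 19 or 23. With at least that many features the fit is exact, so in-sample R2 = 1.00 for every row of the table. With fewer independent noise features, p, expected R2 is p/(n - 1). For the 11 measures with no sensor or band split this is 11/19 = 0.58 at n = 20 and 11/23 = 0.48 at n = 24; simulation gave 0.59 and 0.48.

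**Best 5 features by correlation, pure noise, n = 20, 463 to 1,254 features** (simulation medians; leave-one-out R2 = 1 - PRESS/SST):
- In-sample R2 is about 0.8 if features are independent, and 0.54 to 0.75 under assumed correlated structures.
- With selection done once outside the loop, leave-one-out R2 for independent features is still 0.55 to 0.64, which is falsely reassuring.
- With selection repeated inside the loop, it is about -0.5 to -0.6 for independent features.

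**What is open in the output.**
- Score: 8 + 2 + 1 = 11 BRIEF scores, 10 PDDBI domains and the PDDBI summary score named in section 6.1, so at least 22 candidates.
- Period: active, sham, pooled, or their difference.
- Window: end of stimulation (weeks 8 and 16) or four weeks later (weeks 12 and 20). Both are scheduled. The baseline and 4-week follow-up wording in section 6.1 belongs to the hypothesis tests and fits either.

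**A feature that tracks only ABA gain.** Assume each period's change is sqrt(rho) x G + sqrt(1 - rho) x noise, where G is the child's ABA gain and rho is the correlation between the two periods' changes. Let the feature correlate r with G and not at all with the tDCS effect. Its correlation with the output is:
- active-period change: r x sqrt(rho), from 0.5 x sqrt(0.3) = 0.27 to 0.7 x sqrt(0.7) = 0.59;
- pooled change: r x sqrt(2 rho/(1 + rho)), from 0.34 to 0.64;
- active minus sham: 0, because G cancels.

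For one feature at unadjusted two-sided 0.05 and n = 20 (20,000 trials per setting), it is significant in 22 to 81%, 32 to 89% and 5% of trials respectively. With Bonferroni over 463 tests, the first two fall to between about 0.2% and 17%.

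**Classifier check.** Accuracy of 12/24 has an exact (Clopper-Pearson) 95% interval of 29 to 71%; 10/20 gives 27 to 73%. These intervals are too wide to support equivalence. Randomisation already makes true baseline accuracy chance, so the exercise tests nothing that is in doubt.

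**The case against.** The best defence is that this is a pilot, that EEG use is described as being piloted, and that prediction is only to be investigated. That stands as regards weight: the analysis is effectively exploratory already. It does not excuse the missing validation rule, because section 6.1 also says the usefulness of EEG will be determined, and the results are meant to justify a larger trial.

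Other points limit what can be claimed:
- A reader might take 463 as a minimum. It is not. The text says only that several scales are used and refers to a study not available here. Two scales would give 159, and the conclusion is the same.
- A reader might infer that the plan puts all features into one linear model. It does not say so; feature-by-feature regression also fits the wording. The R2 of 1.00 is conditional on the single-model reading.
- A reader might conclude that no validation exists anywhere. Some pages were removed before review, and the cited study may describe validation. The statement is only that the available text adopts none for this regression.
- Bonferroni is required, and its natural family is the features tested. Not stating the number of tests is a missing detail, not an error. The rule sits with the active-versus-sham comparisons, and nothing says that it governs the regression.

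**Conclusion.** The concern holds for Aim 2. With 159 to 1,254 candidate features and at most 20 to 24 children, in-sample performance says nothing about prediction, and the available text offers no other measure. The direction does not depend on the feature count or on feature correlation; the exact R2 values do.

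The output is not defined tightly enough to separate response to tDCS from gain under ABA. The 22 to 89% range illustrates this under assumed correlations (0.5 to 0.7 for the feature, 0.3 to 0.7 between periods) and an unadjusted 0.05. It should not be read as this trial's false-positive rate. The classifier equivalence claim is invalid as worded.

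A reader might infer that the trial's main result is compromised. The documents do not support that: the primary BRIEF comparison does not use the EEG regression.

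**What to change.** 1. **Model and validation.** Use a penalised model, or a small set of summary features chosen before unblinding (averaging over sensors gives 6 x 4 + 7 = 31). Report leave-one-child-out R2 (1 - PRESS/SST) with a permutation P value, with all selection and tuning inside the loop. Hold out all of a child's segments together: the stated recordings of 1 to 5 minutes yield 2 to 10 segments of 30 seconds.
2. **Output and input.** Use each child's active-minus-sham difference in change of one pre-named BRIEF score, adjusted for sequence. State the window as an explicit choice; weeks 4 to 8 and 12 to 16 are already scheduled. For prediction, use week-4 EEG, which precedes all stimulation in both orders. For association, use the active-minus-sham difference in EEG change.
3. **Baseline.** Replace the classifier equivalence claim with a descriptive comparison of baseline EEG by sequence.

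**Cost.** Only SAP wording and analysis code change; no new data or visits are needed. Reported performance will look less favourable, and precision is limited. At n = 20, 80% power needs a correlation of about 0.58 for one pre-chosen feature and about 0.75 for 31 features with Bonferroni. The active-minus-sham output has sqrt(2(1 - rho)) times the SD of a single-period change: 1.18 times if the two periods' changes correlate 0.3, and 0.77 times at 0.7.

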Aim #1: To pilot the use of tDCS to children with ASD enrolled in ABA programs. We intend to provide the stimulation during the ABA therapy sessions focused on preselected cognitive programs and measure the outcome via a standardized instrument, and we will also use discrete acquisition data compiled as part of the students programming.

There is accumulation evidence that tDCS is effective in treating the core symptoms of ASD as well as co-morbidities, but there are still gaps in our knowledge. Nearly all the existing studies were done on high functioning adults with ASD. The larger double-blind studies utilized general ASD outcome measures and specific comorbid symptoms were not examined, especially in combination with evidence-based intervention in a natural environment setting. This research study further our understanding of the benefits of tDCS in treating the comorbidities and core symptoms in children with ASD.

Aim #2: To evaluate a biomarker of brain complexity at various points (before, during, and after the treatment) obtained through EEG measurements. We will use portable EEG devices which can be used in the therapy session. We hypothesize that through this treatment, circuits will be made more functional and this will be associated with increased complexity measured on the EEG, which has been shown to be associated with typical functioning when compared to ASD brainwaves.

EEG data will be obtained and analyzed for complexity with a unique algorithm previously successful in separating ASD from controls and predicting outcome in children as young as 3 months old ([name], Tierney et al., 2011; [name], Tager-Flusberg et al., 2018). The question of whether this will be predictive (at baseline) or associated with clinical improvement will be investigated.

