In addition, we will be piloting the use of EEG prior to treatment as a digital biomarker which could predict response to the tDCS, and we will get EEGs before and after each arm of treatment/. We will be using an algorithm which measures EEG complexity and this method has been shown to be highly predictive of ASD from non-ASD in children as early as 3 months of age ([name], Tager-Flusberg et al., 2018). See preliminary data.

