4.0 Subject Considerations

4.1 Subject Selection and Enrollment Considerations

1. Method to Identify Potential Subjects: Participants will be recruited from the local New Jersey ABA providers or healthcare providers in New Jersey. New Jersey has one of the highest rates of autism in the United States. Based on the gender distribution of ASD in the population, we expect that our group will be approximately 75% male) but will include subjects from ethnic groups representative of NJ counties. We do not anticipate challenges related to recruitment.

2. Recruitment Details:

- a. Identify Potential Subjects- We will begin with a kickoff meeting with local ABA providers to discuss the study with the PI Co-Investigators and study coordinator. The meeting will be virtual using WebEx. We will also publish an informational study flyer with general study details and contact information for the study coordinator. The flyer will be distributed to ABA providers or used to publish on RWJ research website, Autism New Jersey, Autism Speaks, ABA provider websites or on other autism websites.
 - A phone line will be set up for families or ABA providers to discuss the study as well as for participants to learn more about the study and set up a telephone screening intake if interested.
 - The Research Coordinator /Research Assistants- will complete a telephone Screening (determine eligibility by inclusion and exclusion criteria). Eligible families considering participation can ask specific questions and discuss specific study details with the research assistant or PI. Information regarding the study will be emailed to participant families to review (consent forms).

3. Inclusion Criteria

- 1. Males and females between 5 and 12 years with autism
- 2. Enrolled in a New Jersey ABA-based program (school or in-home) supervised by a Board-Certified Behavior Analyst (BCBA)
- 3. Stable medical and behavioral treatments for at least 4 weeks prior to, and during the study

4. Able to tolerate wearing tDCS as determined during a week-long daily desensitization training.

4. Exclusion Criteria

- 1. Any implanted metal device (heart pacemaker, cochlear implant, surgical clips, etc.)
- 2. Severe neurological disorders such as TBI, brain tumor, intracranial infection
- 3. Seizure disorder with a seizure within the last two years
- 4. Skull defect
- 5. Peripheral blindness or deafness

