4.2 Secondary Subjects N/A

4.3 Number of Subjects

A. Total Number of Subjects

- Total number of subjects screened = 30
- Total Number of Subjects eligible: 24 participants eligible and enrolled
- Required Number of Subjects to Complete Research: 20 participants to complete.

B. Total Number of Subjects If Multicenter Study N/A

C. Feasibility

Given the number of participants receiving home-based ABA therapy in NJ, we do not anticipate difficulty with recruitment.

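### The Aim 2 EEG regression has no age term, no pre-phase score and no reference model, so it cannot show that EEG adds information beyond them

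*Combined protocol and SAP*

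**What the plan says.** Section 6.1, under the EEG biomarker subheading, states that "regression models will be computed using the nonlinear EEG features as input variables and the change in assessment scores as output", and then that "Linear regression and machine learning regression models will be used". This is the only description of the model. Nothing elsewhere in the supplied text adds age, the pre-phase score or a covariate-only comparison model. The baseline t-tests and EEG classifiers in the same section compare the two treatment orders and do not enter this regression.

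The purpose is set out earlier. Section 1.2 speaks of "piloting the use of EEG prior to treatment as a digital biomarker which could predict response to the tDCS". Section 1.1 says: "The question of whether this will be predictive (at baseline) or associated with clinical improvement will be investigated". The same section expects "increased complexity measured on the EEG, which has been shown to be associated with typical functioning when compared to ASD brainwaves".

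The missing variables are available. Section 4.1 admits "Males and females between 5 and 12 years with autism", and the schedule tables in Sections 1.3 and 1.10 place the BRIEF and PDDBI at weeks 4 and 12, before each stimulation phase.

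**The concern.** A candidate biomarker is useful if it tells the investigator more than age and a short parent questionnaire already do. The planned model never makes that comparison.

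There are two routes by which an uninformative feature could look predictive. First, a change score contains the pre-phase score with a negative sign, so a feature that moves with that rating can correlate with change without carrying any further information. Second, ages run from 5 to 12, and if both an EEG feature and the rate of change vary with age, the feature can stand in for age.

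Sections 1.5 and 1.6 say the biomarker data are meant to help justify an adequately powered trial, so a marker of age or of the starting rating could be carried forward as a marker of response.

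**Working it through.** The plan gives no effect size, standard deviation or correlation for this analysis, so it has no figure to reproduce. The sizes below are illustrations.

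**Inputs from the documents.** 20 completers (Section 4.3: "Required Number of Subjects to Complete Research: 20 participants to complete") and 24 enrolled; significance level 0.05 (Section 6.1), taken as two-sided because sidedness is not stated.

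**Assumed inputs.** Correlation r between one EEG feature and the pre-phase score, 0.3 to 0.7; test-retest correlation ρ of the score, 0.5 to 0.8; equal variance before and after; no treatment effect.

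**Mechanism A: the feature follows the observed pre-phase rating, or a state that drifts back.** Given the pre-phase score, the feature tells nothing about the end-of-phase score. Then

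corr(pre, change) = −√((1 − ρ)/2), and corr(EEG, change) = −r × √((1 − ρ)/2).

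- Weakest case (r = 0.3, ρ = 0.8): −0.3 × 0.316 = −0.095.
- Middle case (0.5, 0.7): −0.5 × 0.387 = −0.19.
- Strongest case (0.7, 0.5): −0.7 × 0.5 = −0.35.

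**Mechanism B: the feature follows only stable severity.** Let pre = severity + error and post = severity + new error. Change is the difference of two errors, so corr(EEG, change) = 0. Given the pre-phase score, however, the feature still carries information on severity that one noisy rating missed:

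partial corr(EEG, post | pre) = [r/√(1 − r²)] × √((1 − ρ)/(1 + ρ)).

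- Weakest: 0.314 × 0.333 = 0.105.
- Middle: 0.577 × 0.420 = 0.24.
- Strongest: 0.980 × 0.577 = 0.57.

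**Simulated rejection rates for one feature (40,000 trials per setting, n = 20).**

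| Mechanism | Change on EEG (as planned) | End score on EEG + pre-phase score |
|---|---|---|
| A: observed rating or drifting state | 6.8% to 33.6% (middle 13%) | 4.8% to 5.3% |
| B: stable severity only | 4.8% to 5.2% (middle 4.9%) | 7% to 75% (middle 17%) |

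With 24 children, the planned model rejects in 7.2% to 39.8% under A (middle 15%). Under B the middle case gives 4.9% as planned and 20% with baseline adjustment.

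**Age (n = 20, 8,000 trials per setting).** For a feature correlated 0.3, 0.5 or 0.7 with age and otherwise uninformative, the unadjusted test rejects in 6.6%, 9.8% or 14.6% if age correlates 0.3 with change, and in 9.6%, 19.5% or 33.1% if that correlation is 0.5. With age in the model the rate is 5.0% to 5.4%.

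**Requiring both models.** A joint rejection cannot be more frequent than the rarer of the two. Under A the adjusted model holds about 5%; under B the change model does. The joint rule is therefore at most about 5% per feature under either pure mechanism.

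**The case against.** The strongest objection is that a change score is not biased merely because a feature correlates with baseline severity. A reader might infer that any such feature must correlate with change, and that adding the pre-phase score restores the 5% rate. The documents support neither step. Under stable severity plus rating error the planned model is sound, and baseline adjustment produces the spurious finding. Nothing in the plan says which mechanism applies. This objection stands, and it rules out baseline adjustment as the sole remedy.

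A reader might also infer that a link between EEG and baseline severity is likely here. Section 1.1 describes separating ASD from typical functioning; every child in this trial has autism, and the primary outcome is executive function. No within-autism correlation is given. This stands too, so the sizes are conditional.

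On age, Section 1.6 says: "Each item score is converted within each scale for computation of T scores". If those scores are age-normed, part of the age effect on level is removed, though not an effect on rate of change. The plan does not say whether T or raw scores enter the change.

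Finally, the absence of covariates is read from silence in a brief account of an exploratory pilot analysis, which also leaves open whether the inputs are baseline EEG or EEG change. That lowers the stakes. It does not supply the missing comparison.

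**Conclusion.** The point holds in a limited form. As written, the Aim 2 regression cannot separate what EEG contributes from what age and the pre-phase rating already give. With 20 children, the unadjusted false-positive rate per feature is roughly 7% to 34% if the feature follows the observed rating or a drifting state, and 5% if it follows only stable severity. In the latter case the baseline-adjusted model alone is wrong, at about 7% to 75%. All these figures rest on assumed correlations (EEG-baseline 0.3 to 0.7, test-retest 0.5 to 0.8) and concern one feature at a nominal 5% level.

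The primary BRIEF comparison is unaffected. The missing sham contrast in the biomarker model and the number of EEG features are separate problems that this point does not resolve.

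**What to change.** Amend the regression text in Section 6.1 to:

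1. Include age in every biomarker model.
2. Fit and report two models for each feature: change on EEG and age; and end-of-phase score on EEG, age and pre-phase score.
3. For machine-learning models, report the out-of-sample gain over a reference model with age and pre-phase score only. This gain carries the same caution as the baseline-adjusted model and should be read beside the change model.
4. Call a feature a predictor only if it holds in both models.
5. State which phase's change is the output, whether the inputs are baseline EEG or EEG change, and whether T or raw scores are used.

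The cost is wording and some analysis time, with no new data. With one record per child and 20 children, residual degrees of freedom fall from 20 − 2 = 18 to 17 in the change model and 16 in the adjusted model. Requiring both models also loses some power, which is acceptable in an exploratory pilot analysis. The 5% bound applies to the two pure mechanisms and is not guaranteed for a mixture of them.
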